7.1.2. Adverse drug reaction

An adverse drug reaction (ADR) is any noxious and unintended response to an investigational medicinal product (IMP) related to any dose with at least a reasonably possible causal relationship with the IMP.

7.1.3. Serious adverse events and serious adverse reactions

A serious AE (SAE) or serious ADR (SADR) is any untoward medical occurrence that

1. Results in death,
2. Is life-threatening at the time of the event
3. Requires inpatient hospitalisation or prolongation of existing hospitalisation, except:
 - Routine treatment or monitoring of the studied indication, not associated with any deterioration in condition (e.g. Cataract formation)
 - Elective or pre-planned treatment for a pre-existing condition that is unrelated to the indication under study and has not worsened since the start of study drug
 - Treatment on an emergency outpatient basis for an event not fulfilling any of the definitions of a SAE given above and not resulting in hospital admission
 - Social reasons and respite care in the absence of any deterioration in the patient's general condition
4. Results in persistent or significant disability/incapacity
5. Is a congenital anomaly or birth defect

6. is medically significant, i.e., defined as an event that jeopardizes the patient or may require medical or surgical intervention to prevent one of the outcomes listed above

Inpatient hospitalisation is defined as any stay in hospital on the part of a trial subject that includes at least one night (midnight to 06:00).

If an AE is classified as an SAE, this is documented on a separate SAE sheet (Serious Adverse Event Report Form) in addition to the standard AE documentation.

SAE, regardless of suspected causality, occurring after the patient has provided informed consent and until 4 weeks after the patient has stopped study participation must be reported to the sponsor or designee within 24 hours of learning of its occurrence.

Any SAEs experienced after this 4-week period should only be reported if the investigator suspects a causal relationship to the respective study treatment.

Recurrent episodes, complications, or progression of the initial SAE must be reported as follow-up to the original episode, regardless of when the event occurs. An SAE that is considered completely unrelated to a previously reported one should be reported separately as a new event.

7.1.4. Unexpected adverse drug reaction

An unexpected ADR is an ADR the nature or severity of which is not consistent with the applicable product information available for the IMP. Expected ADRs are listed in the appropriate reference documents (for Ranibizumab/Lucentis®: Summary of product characteristics).

7.1.5. Suspected unexpected serious adverse reactions

A suspected unexpected serious adverse reaction (SUSAR) is an adverse event the nature or severity of which is not consistent with the product information available for the IMP, is regarded as serious, and has at least a possible causal relationship with the IMP.

7.2. Documentation and follow-up of adverse events

The sponsor ensures that all persons involved in the treatment of trial subjects are adequately informed of the responsibilities and actions required when AEs occur. Trial subjects will be asked at each visit whether they have experienced AEs or SAEs. AEs will be documented in the trial subject's medical records and in the trial database/CRF.

For the procedure of SAE-reporting see section 7.3 and section 7.1.3.

7.2.1. Documentation of adverse events and adverse drug reactions

All AEs occurring during the defined reporting period will be documented in the trial database/CRF including all information listed below.

The AE is documented including the following information:

- Date and time of onset and resolution
- Severity
- Causal relationship with IMP / study treatment
- Seriousness
- Interruption or withdrawal of study treatment and other measures taken

Regardless of whether a causal relationship between the AE and the IMP is suspected, trial subjects who develop adverse events must be monitored until all symptoms have been subsided, pathological laboratory values have returned to pre-event levels, a plausible explanation is found for the AE, the trial subject has died, or the study has been terminated for the trial subject concerned.

Preexisting diseases (before administration of the IMP) are not documented as adverse events but as concomitant diseases. New diseases and preexisting diseases that worsen during the trial are documented as AEs.

7.2.2. Severity of the adverse event

The investigator will classify the severity of AEs as follows:

- Mild: clinical symptoms or signs that are well tolerated
- Moderate: clinical symptoms or signs that are enough to impair everyday activities
- Severe: clinical symptoms or signs that markedly impair the trial subject and result in inability to work or go about everyday activities

7.2.3. Causal relationship between adverse event and investigational medicinal product

The investigator will assess for every AE whether a causal relationship with the IMP can be assumed or not. The assessment includes consideration of the nature and type of reaction, the temporal relationship with the IMP, the clinical status of the trial subject, concomitant medication and other relevant clinical factors. If the event is considered due to lack of efficacy or as a symptom or sign of the underlying disorder, no causal relationship will be assumed.

The following definitions are used to assess the causal relationship between all AEs and the IMP (WHO Causality Assessment of Suspected Adverse Reactions):

- Certain: A clinical event, including laboratory test abnormality, occurring in a plausible time relationship to drug administration, and which cannot be explained by concurrent disease or other drugs or chemicals. The response to withdrawal of the drug (dechallenge) should be clinically plausible. The event must be definitive pharmacologically or phenomenologically, using a satisfactory rechallenge procedure if necessary.
- Probable/likely: A clinical event, including laboratory test abnormality, with a reasonable time sequence to administration of the drug, unlikely to be attributed to concurrent disease or other drugs or chemicals, and which follows a clinically reasonable response on withdrawal (dechallenge). Rechallenge information is not required to fulfill this definition.
- Possible: A clinical event, including laboratory test abnormality, with a reasonable time sequence to administration of the drug, but which could also be explained by concurrent disease or other drugs or chemicals. Information on drug withdrawal may be lacking or unclear.
- Unlikely: A clinical event, including laboratory test abnormality, with a temporal relationship to drug administration which makes a causal relationship improbable, and in which other drugs, chemicals or underlying disease provide plausible explanations.
- Conditional/unclassified: A clinical event, including laboratory test abnormality, reported as an adverse reaction, about which more data is essential for a proper assessment or the additional data are under examination.
- Unassessable/unclassifiable: A report suggesting an adverse reaction which cannot be judged because information is insufficient or contradictory, and which cannot be supplemented or verified.

An ADR is suspected if the causal relationship is at least 'possible' or 'conditional/unclassified' or 'unassessable/unclassifiable'. Events assessed as 'unlikely' are not suspected ADRs.

If an ADR is considered a SUSAR it has to be reported as described in sections 7.3.3 - 7.3.7.

7.3. Reporting of serious adverse events, pregnancy, SUSARs and changes in risk-benefit assessment

7.3.1. SAE and pregnancy reporting (investigator to the sponsor)

Regardless of the assumed causal relationship, every SAE that occurs during a trial must be documented in the appropriate part of the trial database/CRF and on an SAE sheet which has to be sent to the sponsor or designee.

Information about all SAEs is collected and recorded on a Serious Adverse Event Report Form which will be provided in the investigator site file. The investigator or a physician who is a member of the local trial team must assess the relationship to study treatment, complete the SAE Report Form in English, and send the completed, signed form by fax within 24 hours to the sponsor or designee. The original copy of the SAE Report Form and the fax confirmation sheet must be kept at the study site. Follow-up information is sent to the same person to whom the original SAE Report Form was sent, using a new SAE Report Form stating that this is a follow-up to the previously reported SAE and giving the date of the original report. The follow-up information should describe whether the event has resolved or continues, if and how it was treated, and whether the patient continued or withdrew from study participation.

SAE reporting is based on regulatory requirements of AMG.

Pregnancies must also be documented on separate pregnancy forms and reported to the sponsor within 24 hours of being made aware of such (see section 7.1.1).

7.3.2. SUSAR reporting

All SAEs are assessed by the sponsor or PCI with regard to seriousness (see Section 7.1.3), causality (see Section 7.2.3) and expectedness (see Section 7.1.4), regardless of the investigator's assessments.

Every SUSAR that becomes known to the sponsor and which was assessed to be likely caused by the use of the trial's IMP in this trial or in another trial that is conducted by the sponsor with the similar IMP (Ranibizumab) will be reported by the sponsor or PCI to the competent supreme federal authority (PEI), the responsible ethics committee and all investigators involved in the study.

A CIOMS-1 format shall be used for submitting expedited reports to the above mentioned partners.

Fatal and life-threatening SUSARs

If a SUSAR is fatal or life-threatening the competent supreme federal authority, the ethics committee responsible and the investigators must be informed by the sponsor or PCI without delay,

at the latest 7 calendar days after becoming aware of the minimum criteria for reporting. In all cases, attempts must be made to obtain further relevant information which must be supplied to the competent supreme federal authority and the ethics committee within a further 8 days.

SUSARs that are not fatal or life-threatening

The investigators and authorities mentioned above will be informed without delay by the sponsor or PCI of all SUSARs, at the latest within 15 calendar days of becoming aware of the minimum criteria for reporting. Further relevant details will be passed on as soon as possible.

If the information at the time of reporting is incomplete, further information to enable adequate assessment of the case will be requested from the reporter or other available sources.

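### The general SUSAR reporting sentence in 7.3.2 asks for a 'likely' causal link, which contradicts the 'possible' threshold in 7.1.5 and 7.2.3 and the unqualified deadline paragraphs of 7.3.2 itself

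*Combined protocol and SAP*

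**What the plan says.** Four places in section 7 of the protocol bear on which SUSARs are reported.

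- **7.1.5 (definition).** A SUSAR is unexpected, serious and "has at least a possible causal relationship with the IMP".
- **7.2.3 (causality scale).** The protocol adopts the six WHO categories. One of them is "Probable/likely: A clinical event, including laboratory test abnormality, with a reasonable time sequence to administration of the drug"; possible is a separate and weaker category. The rule for suspicion is: "An ADR is suspected if the causal relationship is at least 'possible' or 'conditional/unclassified' or 'unassessable/unclassifiable". Only events rated unlikely are excluded. For a SUSAR, the section then says that "it has to be reported as described in sections 7.3.3 - 7.3.7".
- **7.3.2 (procedure).** It opens with the assessment step: "All SAEs are assessed by the sponsor or PCI with regard to seriousness (see Section 7.1.3), causality (see Section 7.2.3"), together with expectedness. The general reporting sentence follows: "Every SUSAR that becomes known to the sponsor and which was assessed to be likely caused by the use of" the trial drug, in this trial or in another of the sponsor's ranibizumab trials, goes to the federal authority, the ethics committee and all investigators. Two deadline paragraphs come after it. The 7-day one begins: "If a SUSAR is fatal or life-threatening the competent supreme federal authority, the ethics committee responsible and the investigators must be informed". The 15-day one speaks of all SUSARs.
- **7.3.3.** The marketing authorisation holder is told about all SUSARs.

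**The concern.** A SUSAR already has a causality test built into its definition. When the reporting sentence adds a second and stricter test, it either narrows the duty or does nothing. Here the added word matches the name of a category on the protocol's own scale, and the sentence just before it sends the assessor to that scale. A sponsor or PCI who applies it literally could decide that a SUSAR rated possible, conditional/unclassified or unassessable need not be sent out.

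At stake is the completeness of expedited safety reports to the authority, the ethics committee and the investigators. Under 7.2.3, a possible event is one that concurrent disease could also explain. In patients with diabetes, serious systemic events can readily fit that description, so the category in question is not a remote one.

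**Working it through.** There is no figure to reproduce; the check is a comparison of the wording.

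**Step 1: the causality threshold in each place.**

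| Place | Threshold | Are possible-rated SUSARs covered? | Are the unclassified and unassessable categories covered? |
|---|---|---|---|
| 7.1.5, definition | at least possible | yes | not named |
| 7.2.3, suspicion rule | all but unlikely | yes | yes, named |
| 7.3.2, general sentence | likely | no, if read on the 7.2.3 scale | no, if read on the 7.2.3 scale |
| 7.3.2, 7-day paragraph | none beyond being a SUSAR | yes | as the SUSAR definition is read |
| 7.3.2, 15-day paragraph | none; all SUSARs | yes | as the SUSAR definition is read |
| 7.3.3, authorisation holder | none; all SUSARs | yes | as the SUSAR definition is read |

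The general sentence in 7.3.2 is the only one out of line. The inclusion of the unclassified and unassessable categories rests on 7.2.3 alone, since 7.1.5 does not mention them.

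**Step 2: do the deadline paragraphs cure it?** In part.

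- For fatal and life-threatening SUSARs in this trial, the 7-day paragraph names the authority, the ethics committee and the investigators, with no qualifier. Read on its own, it is complete.
- For other SUSARs, the 15-day paragraph names the investigators and the authorities mentioned earlier. It does not expressly name the ethics committee. Only the general sentence does so for these cases, and that sentence carries the qualifier.
- SUSARs from the sponsor's other ranibizumab trials appear expressly only in the general sentence.
- The general sentence says what is reported and to whom. The later paragraphs can be read as independent duties, or as deadlines for reports that the general sentence has already triggered. The text does not say which.

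**Step 3: the pointer in 7.2.3.** It sends the reader to 7.3.3 - 7.3.7. The procedure and both deadlines are in 7.3.2, which the range leaves out. Section 7.3 ends at 7.3.5, so 7.3.6 and 7.3.7 do not exist. Within the range, 7.3.3 (authorisation holder) and 7.3.4 (risk-benefit review, including SUSARs in subjects who have completed follow-up) are relevant; 7.3.5 is marked not applicable.

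**The case against.** The strongest reply is that this is loose drafting and that the rest of the text points to full reporting. The deadline paragraphs are unqualified, and a sponsor following 7.3.2 must satisfy them too. Section 7.2.3 says that a SUSAR has to be reported, without any further condition. Section 7.3.2 sets its word in plain text and does not use the full category label, whereas 7.2.3 puts category names in quotation marks when it means them. There are other safeguards: every SAE goes to the sponsor within 24 hours whatever its causality, the sponsor or PCI reassesses all SAEs, the authorisation holder is notified of SAEs, and an annual safety report goes to the authority and the ethics committee.

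Much of this stands, and it rules out three stronger readings that a reader might infer:

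- *That possible and unclassified SUSARs would go unreported.* The documents do not support this, because the 7-day and 15-day paragraphs of the same section have no such limit. They could be left out under one reading.
- *That a fixed share of reports would be lost.* Six categories are listed, five count as suspected, and two are at likely or above, so a reader might infer a loss of three in five. That counts labels and not events, and it ignores the deadline paragraphs. The documents give no SUSAR rate and no distribution over the categories.
- *That the absence of a Data Monitoring Committee removes a second safeguard.* Nothing in the documents would give such a committee a part in sending SUSARs to authorities.

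The reply does not remove the contradiction. It depends on readers preferring one paragraph over another, it leaves the two gaps in step 2 open, and an annual report does not replace a report due in 7 or 15 days.

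**Conclusion.** The point holds as an internal contradiction in an operative safety rule. The general sentence of 7.3.2 conflicts with the definition in 7.1.5, with the suspicion rule in 7.2.3 and with the deadline paragraphs that follow it. On a literal reading, SUSARs rated possible or unclassified could be left out of expedited reports. This is clearest for ethics committee reports of non-fatal SUSARs and for SUSARs from the sponsor's other ranibizumab trials.

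The mismatch of wording and the faulty pointer are certain from the text. The consequence is conditional: it assumes that the word is read on the 7.2.3 scale and that the general sentence is taken as the trigger for reporting. No number of affected reports can be derived. There is no effect on the primary analysis, sample size, power or type I error. It should be corrected, because the rule is wrong as written and is easily put right.

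**What to change.** 1. In the general sentence of 7.3.2, delete the 'likely' qualifier, or replace it with the threshold of 7.1.5 and 7.2.3, so that every SUSAR is reported to the authority, the ethics committee and the investigators. If it is simply deleted, the duty rests on 7.1.5, which does not name the conditional/unclassified and unassessable categories; a reference to 7.2.3 in the same sentence would settle that.
2. In 7.2.3, change the pointer from 7.3.3 - 7.3.7 to 7.3.2 - 7.3.4. Pointing to 7.3.2 alone would drop the notice to the authorisation holder and the rule on SUSARs after follow-up, which the present pointer does reach.

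The cost is two text edits. The downside is possibly a few more expedited reports. Design, data collection and analysis are unchanged.

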7.3.3. Informing the marketing authorisation holder

Novartis Pharma as the marketing authorization holder of the IMP will be notified for SAEs. The sponsor or PCI will also inform the marketing authorization holder about all SUSARs including information reported to the competent supreme authority and ethics committee in accordance with contractual agreements.

7.3.4. Review and reporting of changes in the risk-benefit ratio

Without delay, and at the latest within 15 days of the decision for the need to do so, the sponsor or PCI will inform the competent supreme federal authority, the ethics committee responsible of any events or factors that mean that the risk-benefit ratio of the IMP has to be reviewed. These consist of especially:

- Individual reports of expected serious ADRs with an unexpected outcome
- A clinically relevant increase in the rate of occurrence of expected SADR
- SUSARs in trial subjects who have already completed the follow-up period of the clinical trial ("end-of-trial visit")
- Factors emerging in connection with trial conduct or the development of the IMP that may affect the safety of persons concerned.

7.3.5. Informing the Data Monitoring Committee

Not applicable

7.4. Annual safety report of trial subjects

Once per year, the sponsor or PCI will supply a report on the safety of trial subjects with all available relevant information concerning patient safety during the reference period to the competent supreme federal authority and to the responsible ethics committee.

The annual safety report will be compiled according to the corresponding ICH guideline E2F „Development Safety Update Report – DSUR“.

The data lock point for the first patient data set to be included and analyzed is determined by the date of the competent's authority's approval to conduct the trial.

The sponsor or PCI will supply the report within 60 days of one year after the reference date (data-lock point). Following reports will be supplied annually.

8. Use of trial findings and publication

8.1. Reports

8.1.1. Interim reports

Section 7.4 describes the requirements for annual reports on the safety of trial subjects.

8.1.2. Final report

The competent authority and ethics committee will be informed within 90 days that the trial has officially ended.

Within one year of the completion of the trial, the competent federal authority and the ethics committee will be supplied with a summary of the final report on the clinical trial containing the principle results.

8.2. Publication

It is planned to publish the trial results, in mutual agreement with the PCI, in a scientific journal and at German or international congresses. Publication of the results of the trial as a whole is intended. Any publication will take account of the 'Uniform requirements for manuscripts submitted to biomedical journals (International Committee of Medical Journal Editors' (ICMJE) [JAMA 1997;277:927-34]).

The trial will also be registered in a public register in accordance with the recommendations of the ICMJE (see also Section 5.3).

Any published data will observe data protection legislation covering the trial subject and investigators. Success rates or individual findings at individual trial sites are known only to the sponsor.

Publications or lectures on the findings of the present clinical trial either as a whole or at individual investigation sites must be approved by the sponsor in advance, and the sponsor reserves the right to review and comment on such documentation before publication.

9. Amendments to the trial protocol

To ensure that comparable conditions are achieved as far as possible at individual trial sites and in the interests of a consistent and valid data analysis, changes to the provisions of this trial protocol are not planned. In exceptional cases, however, changes may be made to the trial protocol. Such changes can only be made if agreed by the sponsor, sponsor's representative, the PCI and biometrician, and all authors of this trial protocol. Any changes to the trial procedures must be made

in writing and must be documented with reasons and signed by all authors of the original trial protocol.

Amendments made in accordance with § 10 Secs. 1 and 4 GCP-Verordnung that require approval are submitted to the ethics committee and the supreme federal authority and will not be implemented until approved. Exceptions to this are amendments made to avoid immediate dangers.

10. References

1. The European Agency for the Evaluation of Medicinal Product. Note for Guidance on Good Clinical Practice (CPMP/ICH/135/95).
2. The European Agency for the Evaluation of Medicinal Product. Note for Guidance Structure and Content of Clinical Study Reports (CPMP/ICH/137/95).
3. EMEA-Guideline On Data Monitoring Committees: EMEA/CHMP/EWP/5872/03 Corr
4. The DAMOCLES Study Group. A proposed charter for clinical trial 2005 data monitoring committees: helping them do their job well. *Lancet* 2005; 365: 711-22
